9.5.2. Sample size for self-control case-series

[figure not shown]
The power of the SCCS analysis depends on the number of cases and the ratio between the duration of the risk and the control periods. With a risk and a control period of 12 months each, the number of cases needed versus the detectable risk ratio (incidence rate ratio) is summarized in Table 4. Figure 4 shows the total number of vaccinated subjects needed to follow-up for 30 months after vaccination versus the number of cases and the background incidence.

Table 4Sample size for a SCCS analysis - Number of cases in vaccinated
subjects versus the incidence rate ratio a

Incidence rate ratio	Total number of cases
1.5	194
2	68
3	29
5	15

Method: sample for case-series analysis based on the signed root likelihood ratio [Musonda, 2006] ^a 80% power using a two-sided test and alpha = 0.05

Figure 4 Population size for a SCCS analysis versus the incidence rate ratio and the background incidence in the general population

Dotted line: target sample size of the exposed cohort

9.6. Data Management

9.6.1. Remote Data Entry instructions

Remote Data Entry (RDE), using a validated computer application will be used by the GSK identified reviewer to enter the information obtained from the free text review and final case ascertainment classification.

In all cases, subject initials will not be collected nor transmitted to GSK. Subject data necessary for analysis and reporting will be entered/transmitted into a validated database or data system. Clinical data management will be performed in accordance with applicable GSK standards and data cleaning procedures.

116239 (EPI-HPV-040 VS UK) Protocol FDA - EMA PASS Final Version 1 No monitoring will be done. The GSK identified reviewer remains accountable for the data entry.

9.6.2. Final study database

The final study database will consist of data extracted from CPRD GOLD and additional data from free text review. The study database will be locked and stored by GSK Biologicals' data management according to GSK Biologicals Standard Procedures.

9.7. Data Analysis

Examples of statistical tables and figure templates are given in Annex 6.

9.7.1. Hypotheses

9.7.1.1. Hypotheses for the cohort analysis

Null hypothesis (H0): the incidence of neuroinflammatory/ophthalmic autoimmune diseases (other autoimmune diseases) in the exposed female cohort is equal to the incidence in the historical non-exposed female cohort (historical cohort).

Alternative hypothesis (H1): the incidence of neuroinflammatory/ophthalmic autoimmune diseases (other autoimmune diseases) in the exposed female cohort is different from the incidence in the historical unexposed female cohort (historical cohort).

These hypotheses will be tested separately for each of the two co-primary endpoints. No alpha adjustment will be done.

The same hypotheses will be tested between the two male cohorts.

9.7.1.2. Hypotheses for the self-control case-series analysis

Null hypothesis (H0): the incidence rate of neuroinflammatory/ophthalmic autoimmune diseases (other autoimmune diseases) in the exposed female cohort is the same during the risk period and the control period.

Alternative hypothesis (H1): the incidence rate of neuroinflammatory/ophthalmic autoimmune diseases (other autoimmune diseases) in the exposed female cohort is different during the risk period and during the control period.

These hypotheses will be tested separately for each of the two co-primary endpoints. No alpha adjustment will be done. These hypotheses will be tested for individual diseases using the specific risk periods provided that at least 10 cases be recorded (with 10 cases for SCCS analysis, we will have 80% power to detect incidence rate of 6 to 8 depending on the risk period versus control period ratio).

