For the SCCS analysis, the incidence rates in the exposed cohort during the risk period will be compared with the incidence rates in the exposed cohort during the control period using a conditional Poisson regression model [Whitaker, 2006].

Analysis of individual disease could also be performed depending on the number of cases (at least 10 cases in both exposed and non-exposed cohorts for each defined risk period).

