9.7.6. Secondary endpoints

The new cases of individual autoimmune disease during the specific period (see Section 9.3.2) will be analysed by descriptive statistics per cohort. Incidence rate during the specific period will be computed per cohort for each individual disease as the total number of new cases divided by the total person-year as for the primary endpoint.

In case of more than 10 cases in the exposed female and unexposed female cohorts, a Poisson regression model will estimate the risk ratio and its 95% confidence interval. The Poisson model will include the number of cases in each cohort as the dependent variable, the exposure status as a binary independent variable and the log-transformed total person-year as an offset. Same analysis will be performed for the two male cohorts.

A SCCS analysis of individual disease will be carried out if there are at least 10 cases of disease in the exposed female cohort and during the total of the risk and the control period. The risk period of each disease is the disease specific period : 2 months, 6 months, or 1 year depending on the disease (see Section 9.3.2), the control period is, 22 months, 18 months, or 12 months, respectively. The risk and the control periods are separated by a 6-month buffer period.

These analyses will not be considered as confirmatory analysis.

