9.7.8. Statistical calculations

All the statistical calculations will be done in SAS 9.2 or higher.

All the statistical tests will be two-sided at alpha level of 0.05.

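### For diseases with 12/12-month periods, the stated 80% power from 10 SCCS cases at a rate ratio of 6 to 8 does not hold at two-sided 5%: an exact test has 69% at a ratio of 8

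*Protocol*

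**What the plan says.** - Protocol 9.7.1.2: individual diseases are tested in the SCCS analysis "provided that at least 10 cases be recorded". In support, 10 cases are said to give "80% power to detect incidence rate of 6 to 8 depending on the risk period versus control period ratio". No alpha adjustment is made.
- Protocol 9.5.2, note to Table 4: "Method: sample for case-series analysis based on the signed root likelihood ratio", with "80% power using a two-sided test and alpha = 0.05".
- Protocol 9.7.8: "All the statistical tests will be two-sided at alpha level of 0.05".
- Protocol 9.7.6: the risk period is "2 months, 6 months, or 1 year depending on the disease", and "the control period is, 22 months, 18 months, or 12 months, respectively". The same section says that these individual-disease analyses are not confirmatory.
- Protocol 9.3.2 assigns two months to Guillain-Barré syndrome and autoimmune haemolytic anaemia, six months to ITP, and one year to every other listed disease.
- Protocol 9.7.5.1: the SCCS comparison is made "using a conditional Poisson regression model". Section 9.7.9.2 adds that no censoring is applied and names a published SAS macro. Neither section says whether the test is likelihood-ratio, Wald, score or exact.

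**The concern.** The 10-case rule decides which diseases receive an SCCS test, and the power statement is its only justification. The formula behind that statement treats the signed-root likelihood-ratio statistic as normal. With 10 cases and equal periods, only eleven outcomes are possible, and the error rates actually attainable near 5% are far apart. The stated power may therefore belong to a test that does not keep the level set in section 9.7.8.

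In a safety study this affects how a null result is read. A reader who sees no significant excess for a 12/12-month disease with 10 cases would take it that an eightfold rate would have been found four times in five. Either the chance was lower, or the test used had about twice the stated false-positive rate.

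**Working it through.** **Inputs.** n = 10 cases (9.7.1.2); two-sided alpha 0.05 (9.7.8, 9.5.2); periods of 12/12, 6/18 and 2/22 months (9.7.6); no censoring (9.7.9.2). With two periods of common length, the conditional Poisson model reduces to X ~ Binomial(10, p) for the number of cases in the risk period. Here r = risk/(risk + control) and p = IRR·r/(IRR·r + 1 − r). Under the null p = r, which is 1/2, 1/4 or 1/12.

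**Step 1: reproduce the protocol's figure.** The signed-root formula is n = (1.960 + 0.842·√B)²/A, with A = 2[p·ln IRR − ln(IRR·r + 1 − r)] and B = (ln IRR)²·p(1 − p)/A.

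- Table 4 (12/12; IRR 1.5, 2, 3, 5): 193.7, 68.1, 28.8 and 14.9, against the printed 194, 68, 29 and 15.
- 12/12 at IRR 8: p = 8/9, A = 2(1.848 − 1.504) = 0.689, B = 4.324 × 0.0988/0.689 = 0.620, so n = (1.960 + 0.842 × 0.788)²/0.689 = 9.99.
- Solving for n = 10 gives IRR 7.99 (12/12), 6.01 (6/18) and 8.10 (2/22).

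The stated range of 6 to 8 is therefore what the cited method yields.

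**Step 2: exact behaviour at 12/12, n = 10.** At 8:2 the likelihood-ratio statistic is 3.855, just above the 3.841 cutoff. The null probability of 8 or more is (45 + 10 + 1)/1024 = 5.47%, so the two-sided size is 10.94%. Because that upper tail alone exceeds 5%, rejecting at 8, 9 and 10 breaks the 5% level even one-sided. Rejecting only at 9 and 10, with the mirror image, has size 2 × 11/1024 = 2.15%.

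At IRR 8 (p = 8/9): P(10) = 0.308, P(9) = 0.385, P(8) = 0.217.

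| Test (12/12, n = 10) | Rejects at | True size | Power, IRR 6 | Power, IRR 8 |
|---|---|---|---|---|
| Likelihood ratio | 0–2, 8–10 | 10.9% | 84% | 91% |
| Exact, mid-p or score | 0, 1, 9, 10 | 2.1% | 57% | 69% |
| Wald | 1, 9 | 2.0% | 36% | 38% |

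Wald omits 10:0 because that split has no finite estimate. At 9:1 its z is ln 9/√(1/9 + 1) = 2.08; at 8:2 it is ln 4/√(1/8 + 1/2) = 1.75. The exact test reaches 80% power at IRR about 11.0.

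**Step 3: the other period ratios, n = 10.**
- 6/18: the exact test rejects at 6 or more (size 2.0%). Power is 78.7% at IRR 6, and 80% is reached at IRR about 6.2. The likelihood-ratio test also rejects at 0 cases, which takes its size to 7.6%.
- 2/22: the minimum-likelihood exact test rejects at 3 or more (size 4.45%). Power is 86% at IRR 8, and 80% is reached at about 6.8. The equal-tailed exact test rejects only at 4 or more (size 0.7%). Its power is 67% at IRR 8, and 80% is reached at about 10.3.

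**Step 4: more than 10 cases, 12/12.** Exact power at IRR 8 is 65% with 11 cases, 86% with 12, 83% with 13, 80% with 14 and 92% with 15. Likelihood-ratio size is 6.5% with 11 cases and 9.2% with 13. With 12 cases the two tests have the same rejection region, with size 3.9%.

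**The case against.** The strongest reply is that the protocol declares its sizing method, the figure follows from it, and the choice of a small-sample test is commonly left to a statistical analysis plan. The 69% is also partly a product of discreteness: the test that gives it has a true size of 2.15%. A randomised test of exactly 5% would add (5 − 2.15)/(10.94 − 2.15) = 0.324 of the 8:2 outcome, giving 0.693 + 0.324 × 0.217 = 76%. The rule says at least 10 cases, and at some higher counts the problem disappears. The analyses are also non-confirmatory.

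Most of this stands and limits the point. A reader might infer an arithmetic slip, but there is none; a large-sample formula is used outside its range. A reader might also infer that the planned tests will double the false-signal rate, or will miss a 10:0 split. The protocol does not support either reading, because it names no SCCS test. The Wald interval in section 9.7.9.1 belongs to the cohort Poisson model. The 10.9% and 38% figures describe tests that could be chosen.

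What the reply does not remove is the power statement, which is in the protocol itself. For 12/12 diseases at 10 cases, even the randomised 5% test falls short of 80% at IRR 8, so leaving the choice of test to a later document does not make the statement true.

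**Conclusion.** The power statement is wrong as written for the 12/12-month diseases, which are most of the list. At exactly 10 cases a test that keeps two-sided 5% has 69% power at IRR 8 (57% at IRR 6) and needs an IRR of about 11 for 80%. The 6/18 statement is within about two percentage points. The 2/22 statement holds with the minimum-likelihood exact test and fails with the equal-tailed one. Writing incidence rate where a rate ratio is meant is a wording slip that Table 4 resolves.

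The result assumes common period lengths for all cases, as the no-censoring rule implies, and exactly 10 cases. The impact is modest. The affected analyses are non-confirmatory, and the co-primary composites do not depend on the 10-case rule. It would go too far to conclude that the study's main comparisons are compromised.

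**What to change.** In section 9.7.1.2:

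- Replace incidence rate with incidence rate ratio.
- For individual-disease SCCS analyses, specify an exact conditional binomial test of risk-period against control-period cases, with the null share set by the period lengths. Obtain the confidence interval by inverting that same test, so that the two cannot disagree. State whether it is minimum-likelihood or equal-tailed; at 10 cases the choice matters for 2/22.
- Restate that 10 cases give 80% power for an IRR of about 11 (12/12), about 6.2 (6/18), and about 6.8 (2/22, minimum-likelihood) or 10.3 (2/22, equal-tailed).

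This costs a short rewording and one standard exact calculation per disease. The 10-case threshold, the data and the design stay as they are. The only loss is a less favourable stated detectable ratio for the 12/12 diseases, and for 2/22 if the equal-tailed test is chosen.

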9.7.2. Analysis Population

9.7.2.1. Population for the cohort design

The study population for the cohort design will comprise all exposed and unexposed subjects that satisfy the inclusion criteria.

9.7.2.2. Population for the SCCS analyses

Only the cases of NOAD recorded in the exposed cohort during either the risk or the control periods will be included in the SCCS analysis.

9.7.3. Subject disposition

Subject disposition will be summarized by cohort and overall by computing:

- Number of screened subjects.
- Number (%) of non-eligible subjects for each of the following reasons of non-eligibility:
 - Diagnostic code of NOAD during the year prior to the reference date (for all cohorts);
 - Subject not actively registered with the practice during the study period (for all cohorts);
 - Subject not flagged as acceptable in CPRD GOLD (for all cohorts);
 - Subject not recorded for at least 12 months within CPRD GOLD at reference date;
 - At least one dose of unspecified HPV vaccine or Gardasil at any time before the reference date(for all cohorts);
 - At least one dose of Cervarix vaccine at any time before the reference date (for unexposed cohorts);
 - The first dose of Cervarix received before 01 September 2008 or after 31 August 2010 (for the exposed female cohort).
- Number of eligible subjects in each cohort.
- After frequency matching for age and for practice-region, number of included subjects in each cohort.

A detailed, comprehensive list of reasons for elimination from exposed and unexposed cohort analyses will be established at the time of data cleaning.

9.7.4. Demographic and baseline characteristics

Demographic and baseline characteristics of all included subjects (age at reference date, region (GP practice), other vaccination during the previous year) will be summarized per cohort and overall, using descriptive statistics.

Frequency tables will be generated for categorical variables.

Mean, standard error, median and range will be provided for continuous variables.

The two female cohorts and the two male cohorts will be compared for their demographic and baseline characteristics using Fisher's exact test or Student t-test.

9.7.5. Analysis of co-primary endpoints

9.7.5.1. Cohort analysis

The primary analysis will compare the incidence rates of the primary outcomes of interest between the Cervarix exposed female cohort and the historical unexposed female cohort. Results will be presented as the incidence rate ratio and the incidence difference. Exposed person-time will be defined as the period between the reference date and the earliest of the following events:

- End of study period (defined as 12 months after the reference date);
- Date of de-enrolment from CPRD GOLD;
- Date of unspecified HPV vaccine or Gardasil or Cervarix for unexposed cohort;
- Date of first diagnosis of the outcome of interest.

Incidence rates for auto-immune diseases will be calculated by dividing the number of cases by person-time. A Poisson regression model will estimate the risk ratio and its 95% confidence interval. The Poisson model will include the number of cases in each cohort as the dependent variable, the exposure status as a binary independent variable, the age-group ([9-18],[18-25]) as a covariate, and the log-transformed total person-year as an offset.

Sensitivity analyses

Sensitivity analyses will be performed:

- Incidence rates for NOAD in the exposed cohort will be calculated after each dose by dividing the number of cases by the total person-time. Exposed person-time will be defined as the period between the date of the dose administration and the earliest of the following events:
 - End of risk period (defined as 6 months after each dose);
 - Date of the next Cervarix dose;
 - Date of de-enrolment from CPRD GOLD;

- Date of unspecified HPV vaccine or Gardasil;
- Date of first diagnosis of the outcome of interest.
- Separate analysis will be performed for subjects younger/older than 18 years.
- Analysis including possible confounding factors (if available): other vaccination, age, region, healthcare resource utilization, categorization will be determined based on the available data.
- In case of more than 5% of NOAD with unknown/incomplete date, a sensitivity analysis will be done including these events as occurring during the risk period. This imputation will be done for the four cohorts.
- The same comparison will be done between the two male cohorts. In case of significant difference between these two male cohorts, the primary analysis will be adjusted for time effect other than Cervarix (see Section 9.7.5.1 for the detailed statistical models).

For the SCCS analysis, the incidence rates in the exposed cohort during the risk period will be compared with the incidence rates in the exposed cohort during the control period using a conditional Poisson regression model [Whitaker, 2006].

Analysis of individual disease could also be performed depending on the number of cases (at least 10 cases in both exposed and non-exposed cohorts for each defined risk period).

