For the SCCS analysis, the exposed female cohort will be followed during a total period of 30 months from the first dose. The risk period will be defined as one year after the first dose, including the six months after the last dose when the full three-dose vaccination course is administered. A control period of the same duration will be defined, excluding the periods after subsequent doses. To control for a possible late effect of the vaccine, the control and the risks period will be separated by a six-month buffer period (Figure 2). For analysis of individual diseases, specific risk period could be defined.

light 2 Och control case series analysis	Figure 2	Self-control	case-series	analysis
--	----------	--------------	-------------	----------

Note: all three doses may not have been administered

The SCCS uses each subject as its own control, preventing virtually all potential confounding factors which do not vary with time (e.g. socio-economic status, gender, location) [Whitaker, 2006]. Additionally, fewer cases are usually required, as compared to a case-control design. The control period is chosen subsequent to the at-risk period. Age bias is not anticipated because the follow-up period is short compared to the age effect on incidence of autoimmune diseases (see Table 1).

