9.2.1. The UK HPV National Immunization Programme

The submitted study is in the UK, which is a country with a high Cervarix vaccine coverage. The recommended schedule in the UK for routine HPV vaccination of all girls at 12 to 13 years of age is [DH, 2008; HPA, 2010]:

- Vaccination at this age starts with a first dose of 0.5ml of Cervarix HPV vaccine
- The second dose of 0.5ml follows one to two months after the first dose
- A third dose of 0.5ml follows at least six months after the first dose

The UK has had sufficient Cervarix vaccination coverage to, in theory, enable data acquisition. A public immunisation programme targeting girls between 12-13 years of age including a catch-up programme for young women up to 18 years was undertaken during the academic year 2008/09. A phased catch-up programme for females born 1 September 1991 to 31 August 1995 during the 2008/09 academic year was completed by the end of the 2009/10 academic year. The programme was delivered largely through secondary schools [Crawford, 2009; Sheridan, 2009; Sheridan, 2010]. In the UK public HPV immunization program (12-13 year olds), HPV vaccination coverage in the UK for 2010/11 was 89.0%, 87.6% and 83.8% for the first, second and third dose respectively [Health Protection Agency, 2012]. The recommended age range for the UK programme matches the age range required by the FDA (9-25 years of age) for the post-licensure safety study.

The study population will be composed of female and male subjects, 9 to 25 years of age, registered in the CPRD GOLD.

The exposed cohort will be composed of female subjects vaccinated with at least one dose of Cervarix, with or without other recommended vaccines.

The unexposed historical female cohort will consist of frequency age-matched and practice region-matched female subjects from the period before the introduction of Cervarix. The unexposed concurrent male cohort will consist of frequency age-matched and practice region-matched by one-year classes (15, 16, 17, etc.) male subjects from the

period after the introduction of Cervarix. The unexposed historical male cohort will consist of frequency age-matched and practice region-matched male subjects from the period before the introduction of Cervarix.

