9.3. Variables

9.3.1. Primary endpoint

• Occurrence of new onset of confirmed⁴ autoimmune disease during the period of one year following administration of the first dose of Cervarix (risk period) among an exposed cohort and during an equivalent time period in the unexposed cohorts for the following two co-primary composite endpoints:

[1] Neuroinflammatory/ophthalmic autoimmune diseases:

- Multiple Sclerosis
- Transverse myelitis
- Optic neuritis
- Guillain-Barré syndrome, including Miller Fisher syndrome and other variants
- Other demyelinating diseases:
 - Acute disseminated encephalomyelitis, including site specific variants: e.g. non-infectious encephalitis, encephalomyelitis, myelitis, myeloradiculomyelitis
 - AI peripheral neuropathies and plexopathies (including chronic inflammatory demyelinating polyneuropathy, multifocal motor neuropathy and polyneuropathies associated with monoclonalgammopathy).
- Auto-immune uveitis

[2] Other autoimmune diseases:

- Systemic lupus erythematous
 - Autoimmune (AI) disease with rheumatologic conditions:
 Rheumatoid arthritis (RA)

⁴ Auto-immune disease diagnosis ascertainment by an expert physician panel (Section 9.4.2).

- Juvenile rheumatoid arthritis (JRA)
- Still's disease
- Psoriatic arthritis
- Ankylosing Spondylitis
- AI haematological conditions:
 - Idiopathic thrombocytopenic purpura (ITP)
 - AI haemolytic anaemia
- AI endocrine conditions:
 - Type 1 diabetes mellitus
 - AI thyroiditis including Hashimoto's disease, Graves' /Basedows' disease
- Inflammatory bowel / hepatic diseases:
 - Crohn's diseases
 - Ulcerative colitis
 - Autoimmune hepatitis

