9.7.10. Conduct of analyses

9.7.10.1. Sequence of analyses

The study feasibility assessment is intended to confirm that the data are of sufficient quality to confirm the diagnoses, and that the target sample sizes can be reached. A brief report of the study feasibility assessment will tabulate the numbers of confirmed diagnoses and the number of vaccinees in the periods considered for the exposed and historical cohort.

The final analyses will be performed according to a two-step schedule:

- 1. Between-cohort analysis will be done when the primary and secondary endpoints occurring during the one-year follow-up period will be available for all subjects and the corresponding database will be frozen.
- 2. The SCCS analysis will be carried out when the primary and secondary endpoints occurring during the 30-month follow-up period will be available for all exposed female subjects and the corresponding database will be frozen.

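### Per-dose sensitivity analysis: dose-3 person-time can run past month 12, while the endpoint, case confirmation and cohort data freeze cover only the first year

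*Protocol*

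**What the plan says.** Protocol 9.7.5.1 has two lists of events that end person-time.

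- **Primary cohort analysis.** The list opens with "End of study period (defined as 12 months after the reference date".
- **Per-dose sensitivity analysis.** The rule is: "Incidence rates for NOAD in the exposed cohort will be calculated after each dose by dividing the number of cases by the total person-time". Person-time starts at each dose and stops at the earliest of "End of risk period (defined as 6 months after each dose", "Date of the next Cervarix dose", de-enrolment, another HPV vaccine, or diagnosis. The 12-month stop is not listed, and no onset window is stated for the cases.

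Four other places set the timing:

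- **9.2.1 (schedule):** "A third dose of 0.5ml follows at least six months after the first dose". No upper limit is given. Dose 2 comes one to two months after dose 1.
- **9.3.1 (co-primary endpoint):** onset "during the period of one year following administration of the first dose of Cervarix (risk period) among an exposed cohort".
- **9.4.2 (case confirmation):** reviewers judge whether onset lies in the study's observation period, which is set at one year from the reference date.
- **9.7.10.1 (sequence), step 1:** "Between-cohort analysis will be done when the primary and secondary endpoints occurring during the one-year follow-up period will be available for all subjects". Step 2, the self-control case-series (SCCS), has its own freeze on 30 months of endpoints in the exposed girls.

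Section 9.1.2 describes the one-year risk period as "including the six months after the last dose when the full three-dose vaccination course is administered".

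**The concern.** A rate is interpretable only if its cases and its person-time come from the same interval. Here the denominator for dose 3 may extend past month 12, while the definitions that normally supply the numerator stop at month 12. Any person-time after month 12 would then be counted with no possibility of an eligible case.

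The error would run in one direction and fall on one dose. On-schedule windows for doses 1 and 2 close well inside the first year, so only the dose-3 rate would drop. With no vaccine effect at all, the results could show incidence falling at dose 3. A real excess after dose 3 could be diluted. This is the only cohort analysis in 9.7.5.1 that estimates rates by dose, and in a safety study a downward error is the unwelcome direction.

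**Working it through.** The protocol states no figure for this analysis, so there is nothing to reproduce. The check is arithmetic on the windows.

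**Inputs**

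- Per-dose window: 6 months, cut at the next dose (9.7.5.1).
- Dose 2 at month 1 to 2; dose 3 at month *m*, with *m* at least 6 (9.2.1).
- Eligible onsets: months 0 to 12 from dose 1, if 9.3.1, 9.4.2 and 9.7.10.1 step 1 govern.
- Assumptions: constant incidence, and no de-enrolment within the window.

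**Doses 1 and 2, on schedule.** Dose-1 person-time stops at dose 2, so it lasts 1 to 2 months. The dose-2 window ends at dose 3 or at month 1 + 6 = 7 to 2 + 6 = 8, whichever is earlier. Both lie inside month 12, so neither is affected.

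**Dose 3, one-year onset limit.** The window is [*m*, *m* + 6]. The part in which a case can count is min(12, *m* + 6) − *m*, or zero if that is negative. For *m* from 6 to 12 this gives

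observed/true rate = (12 − *m*)/6.

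| Dose 3 at month | Window ends at month | Months in which a case can count | Observed/true |
|---|---|---|---|
| 6 | 12 | 6 | 6/6 = 1.00 |
| 7 | 13 | 5 | 5/6 = 0.83 |
| 8 | 14 | 4 | 4/6 = 0.67 |
| 9 | 15 | 3 | 3/6 = 0.50 |
| 12 | 18 | 0 | 0/6 = 0 |

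**Assumed spreads of dose-3 dates.** The ratio is linear in *m*, so a uniform spread takes its value at the mean month:

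- months 6–7: (12 − 6.5)/6 = 0.92
- months 6–8: (12 − 7)/6 = 0.83
- months 6–9: (12 − 7.5)/6 = 0.75
- months 6–12: (12 − 9)/6 = 0.50

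**Illustration.** If every dose 3 fell at month 8, a true 1.5-fold rate after dose 3 would appear as 1.5 × 4/6 = 1.0.

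**Dose 3, onsets counted to 6 months after the dose.** Cases and person-time then share the same 6 months: 6/6 = 1.00 for any *m*.

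**Dose 3, person-time also stopped at month 12.** Both cover 12 − *m* months, so the ratio is 1.00 for any *m* below 12. The person-time left is 6, 5, 4, 3 and 0 months for dose 3 at months 6, 7, 8, 9 and 12.

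**The statement in 9.1.2.** Six months after dose 3 fits within one year only if *m* + 6 ≤ 12, that is, *m* ≤ 6. Under the schedule in 9.2.1, that means dose 3 exactly at month 6.

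**The case against.** The strongest reply is that 9.7.5.1 never limits the per-dose cases to 12 months. It gives this analysis its own risk period, and a natural reading is that cases and person-time share it; dropping the 12-month stop would then be deliberate. The data could also exist. Sections 9.1.2, 9.7.9.2 and 9.7.10.1 plan 30 months of follow-up for the same girls. First doses end on 31 August 2010 (9.2.4.1), so 30 months ends around February 2013, before data collection starts on 30 September 2013 (section 6). The step 1 freeze is worded for between-cohort analysis, whereas the per-dose rates use the exposed cohort alone. And 9.4.2 cannot be a hard limit in exposed girls, because the SCCS control period begins at month 18 and needs confirmed cases.

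Much of this stands. A reader might infer that the dose-3 rate is biased low by construction. The documents do not support that: the one-year numerator is an inference from other sections, the 30-month data would remove the bias, and even under the one-year reading the bias is nil for dose 3 at month 6.

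It does not remove the point. The per-dose analysis sits under the cohort analysis of the co-primary endpoints, whose definition is one year. Nothing assigns the 30-month data to it; they belong to step 2. Section 9.4.2, as written, gives later onsets no route to confirmed status. That the SCCS needs such a route shows a conflict to resolve, not that it has been resolved.

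Late risk after dose 3 is also examined in the SCCS sensitivity analysis with individual risk periods (9.7.9.2). That lowers the stakes but does not correct the per-dose cohort rates.

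**Conclusion.** The point holds conditionally. The per-dose stop list allows dose-3 person-time beyond month 12, while the endpoint, the confirmation question and the cohort-step freeze stop there. If those one-year definitions supply the cases, the dose-3 rate is too low whenever dose 3 falls after month 6. The error is nil at month 6, about 17% at month 7, 33% at month 8 and 50% at month 9, assuming constant incidence and full follow-up. Dose-3 dates are not given, so this is a range and not an estimate for this cohort. If confirmed onsets from the 30-month data are used, there is no bias.

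The co-primary comparison is unaffected, because its person-time carries the 12-month stop. A reader should not infer from this point that the main result is distorted.

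Separately, the statement in 9.1.2 that one year covers the six months after the last dose of a full course is too broad for the schedule in 9.2.1.

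**What to change.** Make cases and person-time in the per-dose analysis cover the same interval, in one of two ways:

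1. **Add the 12-month stop.** Put "End of study period (defined as 12 months after the reference date" on the per-dose stop list. This needs no new data. The cost is person-time in late recipients: a third of the dose-3 window for dose 3 at month 8, and all of it at month 12.
2. **Use the longer follow-up.** State that the per-dose analysis counts confirmed onsets up to 6 months after the last dose, taken from the 30-month data on the exposed cohort. This keeps all dose-3 person-time. The cost is that the analysis waits for the second freeze, and the one-year confirmation window in 9.4.2 must be reconciled with the 30-month follow-up, which the SCCS requires in any case.

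Under either option, correct 9.1.2 to say that one year from the first dose includes the full six months after the last dose only when dose 3 is given by month 6. A table showing the share of exposed girls for whom this holds would let readers judge its importance.
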